9.1.2 Definition of a DLT

Stage A1

DLTs will be defined as per NCI CTCAE v4.03 and include:

- Absolute neutrophil count (ANC) $<0.5 \times 10^9/L$ for >7 days
- Febrile neutropenia (fever of unknown origin without clinically or microbiologically documented infection) (ANC $<1.0 \times 10^9/L$, fever $\geq 38.5^\circ C$) lasting >3 days
- Infection (documented clinically or microbiologically) with Grade 3 or 4 neutropenia (absolute neutrophil count $<1.0 \times 10^9/L$)
- Platelets $<25 \times 10^9/L$
- Clinically significant bleeding attributed to grade 3 thrombocytopenia or requiring platelet transfusion
- Grade ≥ 3 oesophagitis onset within 2 weeks of starting radiotherapy
- Grade ≥ 3 pneumonitis onset within 3 months of starting radiotherapy
- Grade ≥ 3 nausea or vomiting not controlled by optimal outpatient anti-emetic treatment
- Grade ≥ 3 diarrhoea despite optimal outpatient anti-diarrhoeal medication use
- Other grade 3 \geq effects thought to be directly treatment related to the combination of M6620 (Berzosertib) with radiotherapy
- Any toxicity causing a delay of radiotherapy completion by greater than one week
- Missing 2 consecutive doses of M6620 (Berzosertib) within a cycle due to Grade ≥ 3 toxicity
- A delay of any of the 3 treatments of 7 days or more within a cycle due to treatment related toxicity
- An elevation of ALT or AST $>5 \times ULN$ lasting 8 days or more
- A concurrent elevation of ALT or AST $>3 \times ULN$ and total bilirubin $>2 \times ULN$ in whom there is no evidence of biliary obstruction or other causes that can reasonably explain the concurrent elevation
- Death due to drug related complications
- Cardiac:
 - QTc prolongation (any QTc interval ≥ 500 msec or any change in QTc interval ≥ 60 msec from baseline) on ECG, unless related to an electrolyte abnormality and prolongation resolves with correction of electrolyte abnormality
 - Any of the following (CTCAE criteria): Grade 2 or greater ventricular arrhythmia (second or third degree AV block), severe sustained/symptomatic sinus bradycardia less than 45 beats per minute (bpm) or sinus tachycardia >120 bpm not due to other causes (e.g., fever), persistent supraventricular arrhythmia (e.g., uncontrolled/new atrial fibrillation, flutter, atrioventricular nodal tachycardia, etc.) lasting more than 24 hours, ventricular tachycardia defined as >9 beats in a row or any length of torsades de pointes (polymorphic ventricular tachycardia with long QTc), or unexplained recurrent syncope
 - Symptoms suggestive of congestive heart failure with confirmed Ejection Fraction (EF) $<40\%$ (by 2D-echocardiogram or Multiple Gated Acquisition [MUGA] scan)
 - Troponin T: level which is consistent with myocardial infarction

Stage A2

DLTs will be defined as per NCI CTCAE v4.03 and include:

- Absolute neutrophil count (ANC) $<0.5 \times 10^9/L$ for >7 days
- Febrile neutropenia (fever of unknown origin without clinically or microbiologically documented infection) (ANC $<1.0 \times 10^9/L$, fever $\geq 38.5^\circ C$) lasting >3 days

- Infection (documented clinically or microbiologically) with Grade 3 or 4 neutropenia (absolute neutrophil count $<1.0 \times 10^9/L$)
- Platelets $<25 \times 10^9/L$
- Clinically significant bleeding attributed to grade 3 thrombocytopenia or requiring platelet transfusion
- Grade ≥ 3 nausea or vomiting not controlled by optimal outpatient anti-emetic treatment
- Grade ≥ 3 diarrhoea despite optimal outpatient anti-diarrhoeal medication use
- Other grade ≥ 3 effects thought to be directly treatment related to the combination of M6620 (Berzosertib) with chemotherapy
- Missing 2 consecutive doses of M6620 (Berzosertib) within a cycle due to Grade ≥ 3 toxicity
- A delay of any of the 3 treatments of 7 days or more within a cycle due to treatment related toxicity
- An elevation of ALT or AST $>5 \times ULN$ lasting 8 days or more
- A concurrent elevation of ALT or AST $>3 \times ULN$ and total bilirubin $>2 \times ULN$ in whom there is no evidence of biliary obstruction or other causes that can reasonably explain the concurrent elevation
- Death due to drug related complications
- Cardiac:
 - QTc prolongation (any QTc interval ≥ 500 msec or any change in QTc interval ≥ 60 msec from baseline) on ECG, unless related to an electrolyte abnormality and prolongation resolves with correction of electrolyte abnormality
 - Any of the following (CTCAE criteria): Grade 2 or greater ventricular arrhythmia (second or third degree AV block), severe sustained/symptomatic sinus bradycardia less than 45 beats per minute (bpm) or sinus tachycardia >120 bpm not due to other causes (e.g., fever), persistent supraventricular arrhythmia (e.g., uncontrolled/new atrial fibrillation, flutter, atrioventricular nodal tachycardia, etc.) lasting more than 24 hours, ventricular tachycardia defined as >9 beats in a row or any length of torsades de pointes (polymorphic ventricular tachycardia with long QTc), or unexplained recurrent syncope
 - Symptoms suggestive of congestive heart failure with confirmed Ejection Fraction (EF) $<40\%$ (by 2D-echocardiogram or Multiple Gated Acquisition [MUGA] scan)
 - Troponin T: level which is consistent with myocardial infarction

Stage B

Acute DLTs will be defined as per NCI CTCAE v4.03 and include:

- Absolute neutrophil count (ANC) $<0.5 \times 10^9/L$ for >7 days
- Febrile neutropenia (fever of unknown origin without clinically or microbiologically documented infection) (ANC $<1.0 \times 10^9/L$, fever $\geq 38.5^\circ C$) lasting >3 days
- Infection (documented clinically or microbiologically) with Grade 3 or 4 neutropenia (absolute neutrophil count $<1.0 \times 10^9/L$)
- Platelets $<25 \times 10^9/L$
- Clinically significant bleeding attributed to grade 3 thrombocytopenia or requiring platelet transfusion
- Grade ≥ 3 oesophagitis onset during induction chemotherapy or within 2 weeks of starting radiotherapy
- Grade ≥ 3 pneumonitis onset within 3 months of starting radiotherapy
- Grade ≥ 3 nausea or vomiting not controlled by optimal outpatient anti-emetics
- Grade ≥ 3 diarrhoea despite optimal outpatient anti-diarrheal medication use
- Other grade 3 \geq effects thought to be directly treatment related to the combination of M6620 (Berzosertib) with chemotherapy or radiotherapy
- Any toxicity causing radiotherapy delivery delay by >3 consecutive fractions
- An elevation of ALT or AST $>5 \times ULN$ lasting 8 days or more
- A concurrent elevation of ALT or AST $>3 \times ULN$ and total bilirubin $>2 \times ULN$ in whom there is no evidence of biliary obstruction or other causes that can reasonably explain the concurrent elevation
- Missing 2 consecutive doses of M6620 (Berzosertib) within a cycle due to Grade ≥ 3 toxicity
- A delay of any of the 3 treatments of 7 days or more within a cycle due to treatment related toxicity
- Death due to drug related complications
- Cardiac:
 - QTc prolongation (any QTc interval ≥ 500 msec or any change in QTc interval ≥ 60 msec from baseline) on ECG, unless related to an electrolyte abnormality and prolongation resolves with correction of electrolyte abnormality
 - Any of the following (CTCAE criteria): Grade 2 or greater ventricular arrhythmia (second or third degree AV block), severe sustained/symptomatic sinus bradycardia less than 45 beats per minute (bpm) or sinus tachycardia >120 bpm not due to other causes (e.g., fever), persistent supraventricular arrhythmia (e.g.,

uncontrolled/new atrial fibrillation, flutter, atrioventricular nodal tachycardia, etc.) lasting more than 24 hours, ventricular tachycardia defined as >9 beats in a row or any length of torsades de pointes (polymorphic ventricular tachycardia with long QTc), or unexplained recurrent syncope

- Symptoms suggestive of congestive heart failure with confirmed Ejection Fraction (EF) <40% (by 2D-echocardiogram or Multiple Gated Acquisition [MUGA] scan) or a relative decrease >20% from screening assessment of EF or if performed within 12 months
- Troponin T: level which is consistent with myocardial infarction

Late DLTs – onset 6 weeks after completion of radiotherapy will be defined as per RTOG/EORTC late toxicity and Mellow Dysphagia score (Appendix C, D):

- Grade ≥ 3 lung and heart toxicity
- Grade 3 oesophageal toxicity with an increase in Mellow score by ≥ 2 since baseline (need to exclude disease progression on CT and/or endoscopy and biopsy)
- Grade 4 oesophageal toxicity

Notes:

- In the event of a Grade 4 neutropenia, a full blood count must be performed no more than 7 days after the onset of the event to determine if a DLT has occurred. Continue to monitor the subject closely until resolution to Grade 3 or less.
- In the event of a Grade 3 or higher elevation in ALT or AST, follow-up laboratory assessments should be performed every 48 to 72 hours until reduced to Grade 2 or less.

9.2 Management of treatment toxicities

In response to a toxicity of unknown or indeterminate causality M6620 (Berzosertib) treatment should be primarily withheld followed by chemotherapy. In the case of M6620 (Berzosertib) or chemotherapy toxicity or dose modification during the concurrent chemoradiotherapy phase patients should continue with RT where possible. The decision as to whether to continue radiotherapy is at the discretion of the treating clinician. If toxicity could be attributable to systemic therapy or radiotherapy, systemic therapy should be withheld first (see section 12.8 for management of radiotherapy toxicities).

Appropriate dose modifications should be considered for all agents if grade 3 or 4 toxicity occurs (see section 9.3 and 9.4 below). In stage A2 dose reductions should not be made beyond 50% of starting dose and the patient should come off study if further Grade 3 or 4 non-haematologic toxicity or Grade 4 haematologic toxicity is then experienced.

9.3 Management of M6620 (Berzosertib) drug toxicities

No dose modifications of M6620 (Berzosertib) may be made (see 9.3.1 for exception in stage A2 below). Treatment may be interrupted because of a non-DLT of Grade 3 or higher, at the discretion of the Investigator. Treatment may be resumed when all toxicities have returned to grade 2 or less, at the discretion of the Investigator. If two consecutive doses of M6620 (Berzosertib) within a cycle are missed due to M6620 (Berzosertib) related Grade ≥ 3 toxicity, this constitutes a DLT, and no further M6620 (Berzosertib) will be administered. Missed doses due to \leq Grade 2 events, will be classified as non-compliance, not a DLT. A delay of any of the 3 treatments of 7 days or more within a cycle due to treatment related toxicity would be considered a DLT.

If the subject misses a dose of M6620 (Berzosertib) for any reason other than toxicity the dose should not be made up and the scheduling should continue as normal, from the next planned dose of M6620 (Berzosertib), unless it is a Tuesday dose which can be made up on the following day (Wednesday). If radiotherapy is withheld for toxicity or other reasons, M6620 (Berzosertib) should also be withheld and the dosing schedule should continue from the next planned dose once radiotherapy has resumed (see also section 8.4).

In Stage A2, if a patient experiences a DLT, they may continue on trial treatment at the next lowest dose level at the discretion of the treating investigator.

In Stage B, if a patient experiences a DLT, the TMG will convene to decide whether it is appropriate for the patient to continue receiving trial treatment, potentially at a reduced frequency of doses.

9.3.1 Additional guidance Stage A2

In stage A2 M6620 (Berzosertib) must not be dose reduced in the first 4 weeks of treatment but doses may be omitted for toxicity (as above). The M6620 (Berzosertib) dose may be reduced after the 4 week DLT window is complete as follows:

1. For Grade 4 hematologic toxicity: dose of M6620 (Berzosertib) to be reduced by 25%.
2. For Grade 3 non-hematologic toxicity: dose of M6620 (Berzosertib) to be reduced by 25%.
3. For Grade 4 non-hematologic toxicity: dose of M6620 (Berzosertib) to be reduced by 50%.

If the dose of M6620 (Berzosertib) has already been reduced by 25% a further dose reduction of 25% may be made to 50% of starting dose. However no further dose reductions may be made beyond 50% of starting dose and the patient should come off study if further Grade 3 or 4 non-haematologic toxicity or Grade 4 haematologic toxicity is then experienced.

9.3.2 Toxicities associated with M6620 (Berzosertib)

Acute hypersensitivity reactions are a toxicity of M6620 (Berzosertib). Serious acute hypersensitivity reactions have occurred during the second M6620 (Berzosertib) infusion in approximately 5% of subjects administered M6620 (Berzosertib) and should be reported as a Serious adverse reaction (see section 8.4 for management of hypersensitivity reactions). In at least one sixth of patient reactions at the site of infusion were noted including erythema, swelling, pruritus. The most common toxicities reported in patients who have received M6620 (Berzosertib) are: fatigue, abdominal pain, diarrhoea, nausea and vomiting, decreased appetite, cough, headache and fever. Almost all instances of these toxicities occurred in patients who were also receiving chemotherapy in combination with M6620 (Berzosertib). M6620 (Berzosertib) in combination with chemotherapy may exacerbate the risks associated with the chemotherapy. The most frequently noted grade ≥ 2 laboratory abnormalities observed (in combination with chemotherapy) are neutropenia, low lymphocytes, low haemoglobin and elevated ALT/AST. M6620 (Berzosertib) absorbs UV-visible radiation spectrum and is widely distributed including to the skin, so subjects should be cautioned to minimise exposure to the sun and other sources of visible and UV radiation and to take protective measures when necessary. Full range of toxicities can be found in the M6620 (Berzosertib) IB.

9.4 Management of chemotherapy toxicities

Toxicity due to capecitabine or cisplatin administration may be managed by symptomatic treatment and/or modification of the dose (treatment interruption or dose reduction) as per standard of care. Once the dose has been reduced, it should not be increased at a later time. Patients taking capecitabine should be informed of the need to interrupt treatment immediately if moderate or worse toxicity occurs. Detailed information can be found in the product SPCs available from www.medicines.org.uk.

9.4.1 Haematological toxicity

Myelosuppression is uncommonly observed with cisplatin and capecitabine. Neutropaenia and thrombocytopenia should be monitored according to the recommended protocol and appropriate dose modifications made. Anaemia may occur cumulatively with cisplatin and should be corrected during radiotherapy to maintain the haemoglobin ≥ 10 g/dL. The FBC should be taken and reviewed (up to 3 days) prior to Day 1 of each cycle of chemotherapy.

Dose modification for haematological toxicities

Neutrophil / platelet count (10^9 /L) (day 1 of subsequent cycles)	Action
ANC ≥ 1 and/or plts ≥ 75	Full dose drugs
ANC 0.5- <1 and/or plts 50- <75 OR any episode of neutropenic sepsis during the previous cycle	Stop chemotherapy until recovery. Restart with 25% dose reduction cisplatin and capecitabine
ANC <0.5 and/or plts <50	Stop chemotherapy until recovery. Restart with 50% dose reduction cisplatin and capecitabine

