8.8 Laboratory values required for administration of chemotherapy

See table in section 8.4.

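### The three rows of the haematology dose-modification table in Protocol 9.4.1 overlap, so one blood result can call for both full-dose chemotherapy and stop-and-reduce

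*Protocol*

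**What the plan says.** The table in Protocol 9.4.1 applies on "day 1 of subsequent cycles" and has three rows (counts × 10⁹/L):

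- Row 1: "ANC ≥ 1 and/or plts ≥ 75". Action: "Full dose drugs".
- Row 2: "ANC 0.5- <1 and/or plts 50- <75 OR any episode of neutropenic sepsis during the previous cycle". Action: stop until recovery, then "Restart with 25% dose reduction cisplatin and capecitabine".
- Row 3: "ANC <0.5 and/or plts <50". Action: stop until recovery, then "Restart with 50% dose reduction cisplatin and capecitabine".

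Neither the table nor its text says which row governs when a patient meets more than one.

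Three other places bear on the same decision. The laboratory table in 8.4 covers both M6620 and chemotherapy. For day 1 of subsequent cycles it gives ANC of at least 1 and platelets of at least 75 in separate rows. Section 8.8, on laboratory values for chemotherapy, says "See table in section 8.4". Section 8.6 says that the laboratory values for chemotherapy follow standard policy and cites 8.4 only for M6620.

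**The concern.** A dose-modification table should turn each blood result into one action. Here row 1 is met when either count is adequate, and rows 2 and 3 are met when either count is low. A patient with one adequate and one low count therefore meets row 1 and a stop row together. ANC 1.2 with platelets 60 fits rows 1 and 2. ANC 0.4 with platelets 80 fits rows 1 and 3.

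Two sites could give different chemotherapy for the same counts and both point to the table. That is first a matter of safety and consistent treatment in Stages A2 and B, the stages that give cisplatin and capecitabine. It may also reach the endpoints: a dose once reduced is not raised again (9.4), Stage B counts patients who complete at least 80% of planned chemotherapy (3.2), and a treatment delay of 7 days or more within a cycle due to treatment-related toxicity is a DLT (9.1.2).

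**Working it through.** **1. Row logic.** The inputs are the three criteria in 9.4.1, with *and/or* read as an inclusive or. Each cell lists every row that the result meets (full = row 1, 25% = row 2, 50% = row 3). No sepsis history is assumed.

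| | Platelets ≥75 | Platelets 50–<75 | Platelets <50 |
|---|---|---|---|
| ANC ≥1 | full | full and 25% | full and 50% |
| ANC 0.5–<1 | full and 25% | 25% | 25% and 50% |
| ANC <0.5 | full and 50% | 25% and 50% | 50% |

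- Full dose together with a stop row: 4 of 9, exactly the cells with one adequate and one low count.
- Both reduction rows: 2 of 9, for example ANC 0.7 with platelets 40.
- One row only: 9 − 4 − 2 = 3 of 9.

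As a diagnostic only, I also read row 1 as needing both counts. The overlaps with full dose fall from 4 to 0, but the 2 overlaps between the reduction rows remain. Row 1 is therefore not the only source of the problem.

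**2. Sepsis history.** Neutropenic sepsis in the previous cycle meets row 2 whatever the counts. With ANC ≥1 and platelets ≥75, such a patient fits rows 1 and 2.

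**3. Against 8.4, 8.6 and 8.8.** Each of the four full-dose overlaps fails one of the two separate requirements in 8.4, so a one-count reading of row 1 contradicts 8.4. But 8.4 says only whether treatment may be given that day, not the dose at restart, so it cannot choose between a 25% and a 50% reduction. Sections 8.6 and 8.8 point to different sources for the chemotherapy values, and no precedence is stated.

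**4. Stage B completion endpoint.** Assumptions: the row is applied once, at cycle 2; the reduction then persists (9.4); nothing else is omitted; planned dose means the protocol dose. From 8.3.2, cisplatin is given in 4 cycles and capecitabine on 42 + 25 = 67 days, of which 67 − 21 = 46 come after cycle 1.

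| Row applied | Cisplatin | Capecitabine |
|---|---|---|
| 1 | 100% | 100% |
| 2 | (1 + 3 × 0.75)/4 = 81.25% | (21 + 46 × 0.75)/67 = 82.8% |
| 3 | (1 + 3 × 0.5)/4 = 62.5% | (21 + 46 × 0.5)/67 = 65.7% |

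Choosing row 1 or row 3 moves the patient across the 80% line. So does choosing row 2 or row 3. Choosing row 1 or row 2 does not, unless further doses are lost.

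**5. Delay DLT, by stage.**

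- A1: no chemotherapy, so the table does not apply.
- A2: the DLT window is 4 weeks (28 days) and cycles last 21 days. The only later day 1 in the window is day 22, and 22 + 7 = 29, at or past its end.
- B: the window is 24 weeks (168 days). Later day 1s fall in weeks 4, 7 and 10 (days 22, 43 and 64), and 64 + 7 = 71, well inside it.

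**The case against.** The best defence is that no careful site would give full dose at a severely low count. Rows 2 and 3 expressly stop chemotherapy when either count is low, and 8.4, through 8.8, requires both counts to be adequate. A reader might infer that the protocol authorises full-dose chemotherapy in severe cytopenia. The documents do not support that: only row 1, read alone, says so, and the stop rows and 8.4 cover every example. What remains is contradictory instructions, with 8.6 leaving it unclear whether 8.4 governs chemotherapy at all.

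A reader might also infer that the trial's DLT count depends on which row a site reads. That is too strong. The link is absent in A1 and marginal in A2. In Stage B it is possible but not established:

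- A stop becomes a DLT under this criterion only if the delay lasts at least 7 days.
- The criterion refers to a delay within a cycle, and the protocol does not say whether postponing the start of a cycle qualifies.
- Section 9.1.1 requires a relation to M6620 or to its interaction with the other treatment.
- ANC below 0.5 for more than 7 days, and platelets below 25, are DLTs in their own right whichever row is used.

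Finally, 9.4.1 calls myelosuppression uncommon with cisplatin and capecitabine, and the documents do not say how often only one count will be low. On the other side, 9.3.2 lists neutropenia among the most frequent grade 2 or higher laboratory abnormalities when M6620 is combined with chemotherapy. The situation is foreseeable, though its frequency is unknown.

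**Conclusion.** The point holds as an internal contradiction in a safety rule. It is not a disputed design choice. Without a sepsis history, 6 of the 9 band combinations are not uniquely classified, and in 4 of those the competing actions are full dose and stop-and-reduce. This rests on reading *and/or* literally. The 4 and 6 count cells of the table, not patients; the documents give no basis for a patient frequency.

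The firm consequence is inconsistent chemotherapy dosing on day 1 of subsequent cycles in Stages A2 and B. The effect on the Stage B completion endpoint follows under the stated assumptions, and turns on whether row 3 is the row applied. The effect on the Stage B delay DLT is only a possibility. Stage A2 also has a completion endpoint, but 3.1.2 does not say which drug its planned dose refers to, so I claim nothing there. The stated sample sizes are unaffected.

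**What to change.** The sponsor should reconcile the table in 9.4.1 with 8.4, 8.6 and 8.8, and say which of them governs chemotherapy on day 1 of subsequent cycles. All three rows should be reworded so that every combination of neutrophil count, platelet count and sepsis history leads to exactly one action. Editing row 1 alone would leave the overlap between the reduction rows and the overlap created by the sepsis criterion. The thresholds, the reductions and the choice of governing rule belong to the sponsor and its clinicians.

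It would help to state in 9.1.2 whether postponing the start of a cycle counts towards the delay DLT. For patients already treated, a listing of day-1 counts with the action taken would show whether sites read the table differently.

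The cost is a text edit to one short table and its cross-references, issued as a protocol amendment. The dose-finding model and sample size need no change.

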9.4.2 Non-haematological toxicity

Gastrointestinal toxicity:

Nausea and vomiting is common following cisplatin, usually starting within 1 hour of treatment and lasting up to 24 hours. Anorexia, nausea and occasional vomiting may persist for up to one week. Nausea occurs less commonly with capecitabine (Diarrhoea occurs with capecitabine and patients should receive advice regarding discontinuation of therapy and use of loperamide or codeine phosphate). Clinicians should be aware of infective causes of diarrhoea (e.g. *Clostridium difficile*), and patients should be tested in cases of concern. Antibiotic treatment is not recommended routinely but may be required in such circumstances. Stomatitis occurs with capecitabine and patients should receive advice regarding good oral care, and the use of mouthwash (e.g. Corsodyl™).

Anaphylaxis: Reactions to cisplatin therapy have been occasionally reported in patients who were previously exposed to cisplatin. Patients who are particularly at risk are those with a prior history or family history of atopy. Serious reactions may be controlled by IV adrenaline, corticosteroids or antihistamines.

Serum Electrolyte Disturbances: Hypomagnesaemia, hypocalcaemia, hyponatraemia, hypokalaemia and hypophosphataemia have been reported to occur in patients treated with cisplatin and hypomagnesemia may occur and should be monitored according to the protocol.

Other Toxicities: Hair loss is not expected with this combination but may rarely occur with most chemotherapeutic agents. Vascular toxicities coincident with the use of cisplatin in combination with other antineoplastic agents have been reported rarely. These events may include myocardial infarction, cerebrovascular accident, thrombotic microangiopathy (haemolytic uraemic syndrome) or cerebral arteritis. There have been reports of optic neuritis, papilloedema and cerebral blindness following treatment with cisplatin.

Non-haematological toxicity dose reductions for Capecitabine and Cisplatin Toxicity	During a course of therapy – Cisplatin and Capecitabine	Dose adjustment for next cycle (% of starting dose)
Grade 1	Maintain dose level for both drugs	100% Cisplatin & Capecitabine
Grade 2		
1 st appearance	Interrupt until resolved to grade 0-1	100% Cisplatin & Capecitabine
2 nd appearance	Interrupt until resolved to grade 0-1	75% Cisplatin & Capecitabine
3 rd appearance	Interrupt until resolved to grade 0-1	50% Cisplatin & Capecitabine
Grade 3		
1 st appearance	Interrupt until resolved to grade 0-1	75% Cisplatin & Capecitabine
2 nd appearance	Interrupt until resolved to grade 0-1	50% Cisplatin & Capecitabine
3 rd appearance	Discontinue treatment permanently	
Grade 4		
1 st appearance	Discontinue permanently Or If physician deems it to be in the patient's best interest to continue, interrupt until resolved to grade 0-1 after discussion with Chief Investigator	50% Cisplatin & Capecitabine

